### 3.4 Definition of dose-limiting toxicity (DLT)

DLT is defined as clinically significant non-hematologic adverse event or abnormal laboratory value assessed as unrelated to disease progression, intercurrent illness, or concomitant medications and occurring during the first cycle on study and at least possibly related to the study drugs that meets any of the following criteria:

- CTCAE Grade 3 AST (SGOT) or ALT (SGPT) for  $\geq 7$  days
- CTCAE Grade 4 AST (SGOT) or ALT (SGPT) of any duration
- Grade 3 nausea/vomiting, dehydration or diarrhea lasting more than 3 days in the setting of optimal supportive medications
- Grade 3 fatigue lasting more than 5 days in the setting of optimal supportive medications
- Grade 3 biochemical abnormalities (e.g., lipase or bilirubin elevation) will only be considered DLT if accompanied by clinical consequences. Grade 3 electrolyte abnormalities will only be considered DLT if possibly related to study drug and not corrected by optimal replacement therapy or if the Grade 3 electrolyte abnormalities persist after 7 days of optimal replacement therapy
- All Grade 4 non-hematologic toxicities of any duration
- For the purposes of DLT assessment, asymptomatic hyponatremia will be “graded” not by the NCI CTCAE version 4.03 but rather by clinically meaningful criterion of  $<125\text{mmol/L}$ . Sodium  $<125\text{mmol/L}$  will be graded as DLT with the exception of asymptomatic translational hyponatremia due to hyperglycemia (see footnote below for calculation).  
*\*In marked hyperglycemia, ECF osmolality rises and exceeds that of ICF, since glucose penetrates cell membranes slowly in the absence of insulin, resulting in movement of water out of cells into the ECF. Serum Na concentration falls in proportion to the dilution of the ECF, declining 1.6 mEq/L for every 100 mg/dL (5.55 mmol/L) increment in*

*the plasma glucose level above normal. This condition has been called translational hyponatremia because no net change in total body water (TBW) has occurred. No specific therapy is indicated, because Na concentration will return to normal once the plasma glucose concentration is lowered. Corrected Sodium (Hillier, 1999) = Measured sodium + 0.024 \* (Serum glucose - 100).*

- All other clinically significant non-hematological adverse event that is Grade 3 according to the NCI CTCAE version 4.03.
- Myelosuppression and cytopenias are expected outcomes of leukemia treatment and per se will not constitute DLT. Only prolonged myelosuppression, as defined by the NCI criteria specific for leukemia, i.e. marrow cellularity < 5% on Day 42 or later (6 weeks) from start of therapy without any evidence of leukemia, will be considered in defining DLT. In case of a normocellular bone marrow with <5% blasts, 8 weeks with pancytopenia will be considered DLT. Anemia will not be considered for the definition of DLT.

Any patients who stop treatment prior to completing evaluation for the DLT observation period (first 28 days) due to disease progression or refusal for further participation for reasons other than toxicity during the DLT defining phase I portion of the study will be replaced at that dose level for a full evaluation of that dose level before a decision regarding dose escalation can be made.

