### 3.0 STUDY DESIGN:

#### 3.1 General

The study will be a phase I/II, single-institution, open-label, non-randomized, parallel group clinical trial. The phase II will include two separate cohorts to be enrolled simultaneously. All patients will be registered through CORE/PDMS.

- **Phase I**
  - This will include FLT3-ITD and –D835 mutated patients with relapsed/refractory AML, including patients who may have been previously exposed to one or more FLT3-inhibitors. Relapsed/refractory status defined by the failure of at least one prior cycle of chemotherapy (including but not limited to cytotoxic chemotherapy, hypomethylator therapy, immune-based therapy, stem cell transplant or stem cell therapy, FLT3-inhibitor therapy, investigational therapy, and others).
  - The DLT assessment period will be performed only during Cycle 1 of Phase I.
  
- **Phase II in two cohorts**
  1. **Cohort 1 (FLT3 inhibitor failure cohort)** in FLT3-ITD and –D835 mutated relapsed/refractory AML who have failed therapy with up to two prior salvage regimens (HSCT or stem cell therapy for patients who previously underwent HSCT/stem cell therapy in remission will not be considered a salvage regimen) and have previously been exposed to at least one prior FLT3 inhibitor.

2. **Cohort 2 (FLT3 inhibitor naive cohort)** in FLT3-ITD and –D835 mutated relapsed/refractory AML who have failed therapy with up to two prior salvage regimens (HSCT or stem cell therapy for patients who previously underwent HSCT/stem cell therapy in remission will not be considered a salvage regimen) with no prior exposure to any FLT3 inhibitor.

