### 3.3 3+3 algorithm

The 3+3 algorithm that we will follow in the phase I is described below.

- Enroll 3 patients at the dose level 0
- Proceed to the next higher dose level with a cohort of 3 patients until at least 1 patient experiences the dose-limiting toxicity (DLT)
- If only 1 of 3 patients experiences the DLT at a given dose level, enter 3 additional patients at the current dose level
- If only 1 of 6 patients experiences the DLT at a given dose level, proceed to the next higher dose level with a cohort of 3 patients or open broadly for phase II if at maximum escalation dose
- If at least 2 of 3 or 2 of 6 patients experience the DLT at a given dose level, then the MTD has been exceeded
- Once the MTD has been exceeded, treat another 3 patients at the previous dose level if there were only 3 patients treated at that dose level

- The MTD is the highest dose level in which we have treated 6 patients with at most 1 experiencing the DLT
- If  $\geq 2/6$  patients experience DLT at dose level -2, the study will be revised to consider additional lower dose levels.

\*With up to 2 potential dose de-escalation level (-1 and -2) to be studied and up to 6 patients to be treated at a given dose, the target maximum number of patients enrolled in the phase I part of the trial will be 12.

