## **5.0 TREATMENT PLAN:**

### **5.1 Schedule**

All patients will be registered through CORE/PDMS.

5.1.1 Selinexor will be administered orally twice a week (e.g. Monday/Wednesday or Tuesday/Thursday or Wednesday/Friday) for 3 weeks of a 28-day cycle. Selinexor will not be dosed the last week of the cycle (week 4). After initiation of sorafenib on cycle 1 day 1, sorafenib will be administered orally daily twice continuously for the duration of the study with no interruptions unless there are adverse events as described in Section 5.2 below. Sorafenib doses will be separated by intervals of approximately 12 hours (+/- 2 hours). Sorafenib will be administered without food, at least 1 hour before or 2 hours after eating. If a dose is missed, the

next dose will not be increased to account for missing a dose. The patient will take the next regular dose at the scheduled time. Patients will receive one cycle of therapy every 28 days (+/- 7 days).

On the day when both drugs, Selinexor and Sorafenib, will be administered:

- Selinexor needs to be taken with food.
- Sorafenib should not be taken with food. Therefore, patient should take Sorafenib at least 1 hour before eating or 2 hours after eating.

**5.1.1.1** Cycles may be started early (but not earlier than day 21) for patients with active disease if judged in the best interest of the patient.

\*For the phase I, DLT defining period is 28 days. As such, cycle 2 should not be started before 28 days for the patients being treated on the phase I cohort to allow for adequate evaluation of DLTs.

**5.1.1.2** Subsequent cycles may be delayed for recovery of toxicity or other medical conditions. Delays in start of subsequent cycles greater than 8 weeks will be acceptable only for patients who are deriving clinical benefit and after discussion with the principal investigator and the sponsor of potential risk/benefit ratio and complete documentation of the degree of clinical benefit and reason for continuation on this regimen.

**5.1.1.3** In instances where one drug has to be discontinued transiently because of safety, the administration of the other drug may continue as scheduled. If the drug that is held can resume at a later time, no doses will be made up and the administration will follow the originally defined schedule calendar according to the drug that was continued.

**5.1.1.4** For patients who discontinue therapy, the reason for treatment discontinuation will be documented.

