### 11.1 Phase I

In order to determine the MTD of selinexor in combination with sorafenib, we will use the standard 3+3 design for dose finding. The MTD is defined as the highest dose level with  $\leq 1$  out of 6 patients experience a DLT during the first 28 days of treatment. **DLT is defined in section 3.4 (page 13)**. The 3+3-dosing algorithm is presented in section 3.3 and the dosing schema for the combination treatment is shown in Table 3. The RP2D will be selected at the end of the phase I portion based on safety and efficacy of selinexor and sorafenib after discussion with the sponsor and the supporting company (Karyopharm). The Investigator is responsible for completing the cohort summary template prior to advancing subjects to the phase II part. Once RP2D has been established, any patients

still on study at a dose lower than RP2D can be dose escalated up to RP2D in accordance with the dose-escalation guidelines in section 5.2.3.

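### The only hematologic DLT cannot be met within the 28 days on which Section 11.1 bases the MTD, while Section 3.3 defines the MTD with no time limit

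*Combined protocol and SAP*

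**What the plan says.** Section 3.4 states that cytopenias as such are not DLTs and makes one exception, prolonged myelosuppression, with two branches. The first is "marrow cellularity < 5% on Day 42 or later (6 weeks) from start of therapy without any evidence of leukemia". The second applies when the marrow is normocellular with under 5% blasts: "8 weeks with pancytopenia will be considered DLT". The starting point of those eight weeks is not given.

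The window is set in several places:

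- Section 3.4, in the replacement rule: "DLT observation period (first 28 days").
- Section 5.1.1.1: "DLT defining period is 28 days".
- Section 11.1, where the MTD is the highest level at which no more than 1 of 6 "patients experience a DLT during the first 28 days of treatment".
- Section 3.1: "The DLT assessment period will be performed only during Cycle 1 of Phase I".
- The lead-in to Section 3.4, which requires an event "occurring during the first cycle on study and at least possibly related to the study drugs".

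Section 3.3 gives the MTD definition without any window: "The MTD is the highest dose level in which we have treated 6 patients with at most 1 experiencing the DLT". Section 11.1 refers the reader to 3.3 for the algorithm and to 3.4 for the DLT definition.

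**The concern.** The protocol clearly intends prolonged marrow failure to be dose-limiting: 3.4 says it is to be considered in defining DLT, and 5.2.3 uses a hematologic DLT as a bar to intra-patient escalation. Yet the section that turns DLTs into an MTD counts only events in a period too short for this one to occur. The MTD is a Phase I primary objective, and the phase II dose, given to up to 40 patients (20 in each of two cohorts), is selected once it is defined. Two statisticians applying 3.3 and 11.1 to the same six patients could declare different MTDs.

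**Working it through.** The plan states no figure to reproduce. The check compares time windows.

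**Gap between window and criterion.**

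- First branch: earliest Day 42; window closes Day 28; 42 − 28 = 14 days.
- Second branch: 8 × 7 = 56 days. If counted from start of therapy, 56 − 28 = 28 days.
- Section 5.1.1 allows a cycle of 28 ± 7 days. Even if the window were stretched to the longest such cycle, 28 + 7 = 35, the gaps would be 42 − 35 = 7 and 56 − 35 = 21 days.

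The cycle-based wording in 3.1 and 3.4 is less decisive than the 28-day wording, because 5.1.1.2 lets cycle 2 be delayed and cycle 1 could then run past Day 42 in some patients. That does not help under 11.1 or 5.1.1.1, which count days.

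**Who has late data when the MTD is decided.** Assume three-patient cohorts entered one after another, each followed for 28 days.

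- MTD is level +1, or a level reached by de-escalation, with six patients entered as 3 + 3: when the last three reach Day 28, the first three are at about 28 + 28 = Day 56. The last three are short by 56 − 28 = 28 days.
- MTD is level 0 with three patients added after +1 was exceeded: the last three are again at Day 28; the first three are at about 28 + 28 + 28 = Day 84.
- MTD is level 0 with six patients treated before +1 was tried: the +1 cohort adds about 28 days, so the last three are also near Day 56. The time is shorter only if two early DLTs stop +1.

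**Size.** The documents give no rate for this event. Both branches require the marrow to be free of leukemia, so the clearance rate is a ceiling. For selinexor, Section 2.2.2 gives (5 + 2 + 2)/63 = 14% for CR, CR(i/p) and MLFS together. Section 2.3 gives 40–50% marrow responses with FLT3 inhibitors, but does not define that term as clearance. Purely as an assumption, if 10–20% of patients who clear stay aplastic or pancytopenic, the event rate p lies between 0.143 × 0.10 = 1.4% and 0.50 × 0.20 = 10%. With the 14% figure alone the upper end is 0.143 × 0.20 = 2.9%.

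The chance that two or more of six patients are affected is 1 − (1−p)^6 − 6p(1−p)^5, which gives 0.6%, 3.3% and 11.4% for p = 2%, 5% and 10%. These values illustrate scale; they are not estimates.

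**Where it matters most.** At a level with no counted DLT, two late events are needed to reach 2 of 6. At a level already at 1 of 6, one late event among the other five is enough.

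**The case against.** The strongest reply is that 3.3 is the operative algorithm. Its MTD definition has no time limit, and read with 3.4 it would count a Day 42 event. This stands as far as it goes. A reader might infer that no rule anywhere counts late myelosuppression toward the MTD; the documents do not support that. What they show is a conflict: 3.3 is silent on time, while 11.1 restates the MTD with a 28-day limit and 5.1.1.1 agrees with 11.1.

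There are also safeguards: Medical Monitor approval of each cohort summary (3.2), RP2D selection on safety and efficacy (3.5), discontinuation of both drugs for prolonged aplasia (5.2.1), the hematologic-DLT bar in 5.2.3, termination for a health hazard (9.2), and SAE reporting to 30 days after the last dose (10.4). They lower the risk, but each depends on judgement, applies to one patient, or only reports an event. None says how a late event enters the count. Phase II monitoring is not a backstop, since Tables 7 and 10 count only non-hematologic toxicity.

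Three other stronger readings should be resisted.

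- That the last three patients are never followed long enough. This is usually untrue when level 0 had six patients before +1 was tried.
- That the event would go undetected. Section 7.2.5 schedules marrows at Day 28 and, nominally, Day 84 (3 × 28), so none is due at Day 42. But the criterion reads Day 42 or later, counts are weekly for three cycles (7.2.2), and 7.2.5 allows extra marrows.
- That the effect is large. At a level already at 1 of 6, 1 − (1−p)^5 gives 10%, 23% and 41% for p = 2%, 5% and 10%. Those figures rest on assumed rates and ignore the late follow-up that the first three patients usually have.

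Section 2.2.2 also reports no DLTs during escalation in the selinexor study that enrolled AML patients. This is mildly reassuring, although that study's DLT definition is not given and sorafenib was not part of the regimen described.

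**Conclusion.** The point holds as an internal inconsistency that makes a rule wrong as written. Under 11.1, prolonged myelosuppression can never count toward the MTD; under 3.3 it could. Followed exactly, 11.1 permits a level to be declared the MTD with at most 1 of 6 counted DLTs while two or more of its patients meet the Section 3.4 definition. The firm sizes are the gaps of 14 and 28 days. The second assumes that the eight weeks run from start of therapy, which the protocol should say, because Section 5.6.3 notes that most patients already have cytopenias at entry. The effect on the chosen dose cannot be quantified from the documents and is probably small. It should be fixed before the MTD is declared, chiefly because of a level sitting at 1 of 6.

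**What to change.** Keep 28 days for non-hematologic DLTs and for escalation between levels. In 3.4, 5.1.1.1 and 11.1, with matching wording in 3.1 and 3.3, state that:

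- prolonged myelosuppression counts toward the assigned dose level through Day 56 from start of therapy;
- the eight weeks of pancytopenia run from start of therapy;
- a level that reaches 2 or more of 6 once late events are included exceeds the MTD;
- the MTD is finalized, and phase II opened, only when the patients at that level have reached Day 56 or become unassessable (progression or new therapy), in which case the 28-day result stands.

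No new restriction on intra-patient escalation is needed. The hematologic-DLT bar in 5.2.3 is enough, and a bar for unresolved cytopenias would catch many patients who entered with them.

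The cost is wording in five sections and a delay of up to 56 − 28 = 28 days, about four weeks, before phase II opens. The delay is shorter, or nil, when level 0 already had six patients before +1 was tested. The weekly counts in 7.2.2 and the unscheduled marrow allowed by 7.2.5 supply the data, so no new scheduled procedure is needed. Dose levels and the pace of escalation do not change.

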### 3.5 Phase II expansion

Once MTD is defined, the RP2D will be selected based on efficacy and safety result from the phase I in discussion with the PI, the sponsor and the supporting company (Karyopharm). The Investigator is responsible for completing the cohort summary template prior to advancing subjects to the phase II portion. The phase II portion will start in two cohorts as defined previously with 20 patients per cohort. Any patients still on study from the phase I portion at a dose lower than RP2D can be dose escalated up to RP2D in accordance with the dose escalation guidelines in section 5.2.3.

However, the dose for any patient may never exceed the RP2D.

## 4.0 PATIENT SELECTION

Patients must have baseline evaluations performed prior to the first dose of study drug and must meet all inclusion and exclusion criteria. Results of all baseline evaluations, which assure that all inclusion and exclusion criteria have been satisfied, must be reviewed by the Principal Investigator or his/her designee prior to enrollment of that patient. In addition, the patient must be thoroughly informed about all aspects of the study, including the study visit schedule and required evaluations and all regulatory requirements for informed consent. The written

informed consent must be obtained from the patient prior to initiating treatment or any study-specific procedures. The following criteria apply to all patients enrolled onto the study unless otherwise specified.

#### 4.1 Inclusion Criteria

##### 4.1.1 Phase I

FLT3-ITD and/or FLT3-D835 mutated patients 18 years of age or older with relapsed/ refractory AML (any number of relapses) including patients who may have been previously exposed to one or more FLT3-inhibitor therapies will be eligible for the phase I portion of this study.

##### 4.1.2 Phase II

**FLT3-ITD and/or FLT3-D835 mutated relapsed/refractory patients:** Patients should have a diagnosis of AML (de novo or transformed from hematologic malignancies). Patients with high-risk myelodysplastic syndrome (MDS) (defined as having  $\geq 10\%$  blasts in the bone marrow) or patients with Chronic Myelomonocytic Leukemia (CMML) (having  $\geq 10\%$  blasts in the bone marrow) may also be eligible after discussion with Principal Investigator (PI).

The patients should have one of the following features:

1. Patients with AML should have failed any prior induction therapy or have relapsed after prior therapy.
2. Patients with high-risk MDS or high-risk CMML should have failed any prior therapy for the MDS or CMML.
3. Patients with MDS or CMML who received therapy for the MDS or CMML and progress to AML are eligible at the time of diagnosis of AML regardless any prior therapy for AML. The WHO classification will be used for AML.

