#### **Phase II**

1. To determine the composite CR (CRc) rate including CR (complete remission) + CRp (complete remission with incomplete platelet recovery) + CRi (complete remission with incomplete count recovery) within 3 months of treatment initiation in FLT3-ITD and –D835 mutated patients with relapsed/refractory AML.

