##### 4.1.3 Patients must be eligible for one of two cohorts:

**Cohort 1 (FLT3 inhibitor failure cohort)** in FLT3-ITD and/or FLT3-D835 mutated relapsed/refractory AML who have failed therapy with up to two prior salvage regimens (SCT or stem cell therapy for patients who previously underwent SCT/stem cell therapy in remission will not be considered a salvage regimen) and have previously been exposed at least one prior FLT3 inhibitor.

**Cohort 2 (FLT3 inhibitor naive cohort)** in FLT3-ITD and/or FLT3-D835 mutated relapsed/refractory who have failed therapy with up to two prior salvage regimens (SCT or stem cell therapy for patients who previously underwent SCT/stem cell therapy in remission will not be considered a salvage regimen) with no prior exposure to any FLT3 inhibitor.

- 4.1.4 Age  $\geq$ 18 years.
- 4.1.5 ECOG Performance Status  $\leq$ 2.
- 4.1.6 Patients should have estimated life expectancy of  $>$ 3 months at study entry.
- 4.1.7 Adequate hepatic (serum direct bilirubin  $\leq$  2.0 x upper limit normal (ULN) (or  $\leq$  3.0 x ULN if deemed to be elevated due to leukemia), alanine aminotransferase and/or aspartate transaminase  $\leq$  3.0 x ULN (or  $\leq$  5.0 x ULN if deemed to be elevated due to leukemia), and renal function (creatinine  $\leq$  2.0 mg/dL).
- 4.1.8 Patients must provide written informed consent.

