## 11.2 Phase II

The primary objective of the phase II is to evaluate the efficacy of the combination. The study has two cohorts (maximum of 20 patients for each cohort): (1) FLT3-ITD and –D835 mutated relapsed/refractory AML previously exposed to any FLT3 inhibitor, and (2) FLT3-ITD and –D835 mutated relapsed/refractory AML with no prior exposure to any FLT3 inhibitor.

For all the cohorts, the primary endpoint is the achievement of CRc (CRc=CR/CRp/CRi) at any time during the first three cycles of therapy and toxicity assessed at the end of one cycle of therapy. CRc and toxicity will be monitored simultaneously using the Bayesian approach of Thall, Simon, Estey (1995, 1996) and the extension by Thall and Sung (1998) separately for each cohort. Multic Lean Desktop (version 2.1) was used to generate the stopping boundaries and the OC tables for futility and toxicity monitoring.

- **Cohort #1: Patients with relapse FLT3-ITD and –D835 mutant AML (FLT3 inhibitor naïve cohort):**

The historical data suggested a CRc rate of 20% for this population and the target CRc with selinexor and sorafenib combination is 35%. The treatment will be considered worthy of further investigation if it elicits an increase in CRc to 35% with acceptable toxicity. A >30% therapy related non-hematological grade 3/4 toxicity rate is considered unacceptable. Given this, we will stop enrollment into this cohort if the observed patients' data suggest that:

- 1)  $\Pr(\text{CR}_{cE} > \text{CR}_{cH} + 0.15 | \text{data}) < 0.025$  or
- 2)  $\Pr(\text{TOX}_E > 0.30 | \text{data}) > 0.90$

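### Phase II eligibility admits high-risk MDS and CMML, but the objective, cohort definitions and historical CRc benchmarks are for FLT3-mutated relapsed/refractory AML, and the analysis pools everyone treated

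*Combined protocol and SAP*

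**What the plan says.** **Planned population.** The phase II primary objective in 1.1 is the CRc rate "within 3 months of treatment initiation in FLT3-ITD and –D835 mutated patients with relapsed/refractory AML". Section 3.1 defines both phase II cohorts as "mutated relapsed/refractory AML who have failed therapy with up to two prior salvage regimens", split by prior FLT3-inhibitor exposure. Section 11.2 sets the benchmarks under headings for relapsed FLT3-mutant AML. For the naive cohort it states "The historical data suggested a CRc rate of 20% for this population", with a target of 35%. For the failure cohort the figures are 10% and 20%.

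**Admitted population.** Section 4.1.2 starts from a diagnosis of AML, then adds that high-risk MDS and CMML, each with at least 10% marrow blasts, may be eligible after PI discussion. Three alternative features follow:
- Item 1 covers AML that failed induction or relapsed.
- Item 2 reads "Patients with high-risk MDS or high-risk CMML should have failed any prior therapy for the MDS or CMML" and does not require AML.
- Item 3 makes treated MDS or CMML that has progressed to AML "eligible at the time of diagnosis of AML regardless any prior therapy for AML".

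**Cohort text in 4.1.3.** Every patient must fit one cohort. Cohort 1 (FLT3-inhibitor failure) requires relapsed/refractory AML. Cohort 2 (naive) reads "mutated relapsed/refractory who have failed therapy with up to two prior salvage regimens", without the word AML.

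**Analysis.** Section 11.3 includes every patient who received any dose in the efficacy analysis. It has no cap, separate benchmark or separate estimate for MDS/CMML.

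Section 11.2 numbers the two cohorts in the opposite order to 3.1 and 4.1.3, so they are called naive and failure below.

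**The concern.** Each phase II cohort is a single arm of at most 20 patients judged against one fixed historical rate. That comparison is interpretable only if the patients counted come from the population the rate describes. A patient with MDS or CMML contributes to the CRc count, to the futility looks at 5, 10 and 15 patients, and to the final estimate. If the expected CRc in such patients differs from that in relapsed/refractory AML, a few of them can move a cohort across a boundary or past its target in either direction. The result would then not answer the question in 1.1.

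The eligibility text is also hard to apply. Section 4.1.2 opens a route for MDS/CMML. Cohort 1 of 4.1.3 closes it. Cohort 2, read literally, leaves it open.

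**Working it through.** **1. Reproduce the plan's figures.** The inputs are from 11.2: CRc prior Beta(0.4, 1.6) against 0.20 + 0.15 = 0.35 (naive); Beta(0.2, 1.8) against 0.10 + 0.10 = 0.20 (failure); stop if the posterior probability is below 0.025. With x responders in n patients the posterior is Beta(a + x, b + n − x).

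| Cohort | n | Posterior probability at x | At x + 1 | Stop if CRc count ≤ |
|---|---|---|---|---|
| Naive | 5 | x=0: 0.0139 | 0.1525 | 0 |
| Naive | 10 | x=1: 0.0215 | 0.1043 | 1 |
| Naive | 15 | x=2: 0.0192 | 0.0728 | 2 |
| Failure | 5 | x=0: 0.0279 | 0.3416 | never |
| Failure | 10 | x=0: 0.0065 | 0.1218 | 0 |
| Failure | 15 | x=0: 0.0017 | 0.0423 | 0 |

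These equal Tables 6 and 9. The toxicity limits are 4, 6, 8 (Table 7) and 4, 5, 7 (Table 10). Exact enumeration over the three looks, with CRc and toxicity independent, gives these early-stopping probabilities at 30% toxicity:
- Naive: 0.5778 at CRc 20% and 0.2384 at 35% (Table 8).
- Failure: 0.4761 at CRc 10% and 0.2820 at 20% (Table 11).

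All match, so the design arithmetic is sound. The issue is which patients it is applied to.

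**2. Chance of reaching the target count.** The yardstick is an observed rate at target: 7/20 = 35% (naive) and 4/20 = 20% (failure). The number of MDS/CMML patients and their CRc q are not in the documents. **Assumption:** 5 of 20, with q over a range. The responder count is Binomial(15, p) + Binomial(5, q), where p is the true CRc in AML.

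| Cohort, p in AML | No added patients | Low q | Higher q |
|---|---|---|---|
| Naive, p=0.20, P(≥7) | 0.087 | q=10%: 0.046 | q=30/40/50%: 0.141 / 0.210 / 0.291 |
| Naive, p=0.35, P(≥7) | 0.583 | q=10%: 0.342 | – |
| Failure, p=0.10, P(≥4) | 0.133 | q=5%: 0.091 | q=20/30/40%: 0.233 / 0.351 / 0.478 |

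The assumed share matters. With 2 of 20 instead of 5 (naive, p=0.20, q=40%), P(≥7) is 0.128 rather than 0.210.

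The failure-cohort row applies only if such patients are admitted to that cohort, because Cohort 1 as worded requires AML.

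**3. Effect on the interim looks.** **Assumption:** a 20% share, so the mean CRc is 0.8p + 0.2q. Toxicity is 30%.
- Naive, p=0.20, q=45%: mean 0.25; early stopping 0.435 against 0.578 (the Table 8 row for 0.25).
- Naive, p=0.20, q=10%: mean 0.18; early stopping 0.641.
- Naive, p=0.35, q=10%: mean 0.30; early stopping 0.322 against 0.238.
- Failure, p=0.10, q=30%: mean 0.14; early stopping 0.374 against 0.476.
- Failure, p=0.20, q=5%: mean 0.17; early stopping 0.320 against 0.282.

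**4. Item 3 of 4.1.2.** The only definition of relapsed/refractory is under the phase I bullet of 3.1. It is failure of at least one prior cycle of chemotherapy, counts hypomethylator therapy, and names no disease. MDS or CMML that was treated and then became AML could meet it with no AML therapy. Nothing says the definition governs phase II, and the 11.2 benchmarks are headed relapsed AML. Item 3 therefore cannot be placed with certainty inside or outside the planned population.

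**The case against.** The strongest reply is that the allowance is a narrow exception. MDS/CMML entry needs PI discussion, possibly nobody will enter by it, and if nobody does, nothing changes. The missing word in Cohort 2 is probably a slip, since 3.1 has AML for both cohorts. Section 11.3 also plans to test response against clinical characteristics, which might show a difference by diagnosis. All this limits the likely size of the problem. It does not remove it: no cap is stated, a test of association does not isolate the relapsed/refractory AML rate, and it does nothing for the interim looks.

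A reader might infer three stronger points that the documents do not support.
- *Item 3 overrides the limit of two salvage regimens.* It does not. Section 4.0 requires all criteria to be met and 4.1.3 requires a cohort, each carrying that limit.
- *Item 3 patients are plainly not relapsed or refractory.* The 3.1 definition could cover them, so this is an ambiguity to resolve.
- *The AML response rules inflate duration of response after PR in low-blast entrants.* Relapse after CR needs only 5% marrow blasts (8.7), so a relapsed AML patient can also enter with a low blast count. Changing MDS/CMML eligibility would not alter that. PR is not among the responder categories listed at the start of section 8, and CRc is unaffected.

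**Conclusion.** The point holds as an inconsistency between sections. The MDS/CMML allowance in 4.1.2 is not carried into the phase II objective, the 3.1 cohorts, Cohort 1 of 4.1.3 or the 11.2 benchmarks. Cohort 2 of 4.1.3 is worded differently from 3.1, and pooling in 11.3 leaves the mismatch in the primary result. That is certain from the text.

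The consequence for CRc is conditional on such patients enrolling. It would be wrong to conclude that the design favours the combination: low-responding patients make a false lead less likely and a real effect easier to miss, while high-responding patients do the reverse. The ranges in the working rest on an assumed 5 of 20 patients (20% for the interim looks) and assumed CRc rates. They show that the effect could be material in a 20-patient cohort, not that it will be. This should be corrected, at modest cost.

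**What to change.** 1. Reconcile 4.1.2 and Cohort 2 of 4.1.3 with 1.1, 3.1 and 11.2, so that all five describe the same disease population.
2. State that the relapsed/refractory definition in 3.1 applies to phase II, and whether it counts therapy given for MDS or CMML before AML. That settles item 3.
3. Choose one of two routes:
   - Limit phase II to relapsed/refractory AML.
   - Keep MDS/CMML patients, but apply the CRc boundaries of Tables 6 and 9 and the primary CRc estimate to relapsed/refractory AML only, and report MDS/CMML response separately. State whether these patients count in the toxicity looks of Tables 7 and 10.

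**Cost.** The first route slows accrual slightly. Under the second, if these patients are enrolled outside the 20 per cohort, the stated total of 52 (12 + 20 + 20) must be adjusted. If they stay within the 20, CRc precision falls slightly. With 15 rather than 20 AML patients at a CRc of 20%, the standard error goes from √(0.2 × 0.8/20) = 0.089 to √(0.2 × 0.8/15) = 0.103. The boundaries themselves need no recalculation.
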